### **Estimated number of subjects to be submitted:**

We estimated that the enrollment of 963 patients in non-STE-MI group would provide the study with a statistical power of 95% to detect a relative excess mortality rate of 5% in ACO-MI subgroup (from 10% to 15%) with the use of a two-sided test at the 0.05 level, with a frequency prediction of 25% for ACO-MI. Far less patients (267 and 383) would be necessary to detect a 10% difference in area under curve (AUC, from 0.700 to 0.770) for the comparison of diagnostic accuracy two approaches in predicting ACO and long-term mortality, respectively.

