### **2. Patient selection**

We planned to enroll 1000 patients in each of the STEMI, NSTEMI and control groups.

Considering [name] Thoracic and Cardiovascular Surgery Training and Research Hospital has a large local network for primary with around 1000-1500 STEMI patients per year referred for primary PCI, it will take approximately one-year period to collect 1000 STEMI patients. This institution also receives STEMI and NSTEMI patients with a 2:1 ratio, which corresponds well to the reported incidences of these two entities. Therefore, we expected to enroll 1000 NSTEMI patients before STEMI group is completed. Another 1000 patients with a clinical picture compatible with an acute coronary event, but without any ECG changes during serial follow-up and negative and unchanging troponin levels within the first 24 hours will be enrolled. As these patients were so much in frequency, and this group would be completed at the beginning of the study, if we started at the same time with

STEMI/NSTEMI enrollment (May 1, 2017); we decided to select these patients from a computer-generated random list. Therefore, the patients in these group was enrolled after first two groups were completed (December 31, 2018). The total admission counts will also be calculated for the weighted analysis of diagnostic accuracy indexes; such as sensitivity, specificity, negative and positive predictive value. After this enrollment period we will have three cohorts.

- STEMI group: These patients should have all of the following criteria: (1) New ST-segment elevation at the J-point in two contiguous leads with the cut-point:  $\geq 1$  mm in all leads other than leads V2–V3 where the following cut-points apply:  $\geq 2$  mm in men  $\geq 40$  years;  $\geq 2.5$  mm in men  $< 40$  years, or  $\geq 1.5$  mm in women regardless of age. (2) a peak troponin level above 99th percentile and (3) a clinical picture compatible with acute coronary syndrome.

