### **Statistical Analysis**

Baseline characteristics will be summarized using standard descriptive statistics. Comparisons of relevant parameters between groups will be performed by chi-square, Fisher's exact test, Mann-Whitney U, Kruskal-Wallis H test, one-way ANOVA and student t-test, as appropriate. Patients with missing values will be excluded pairwise from analyses. A Cohen's  $\kappa$  test will be used for determination of the intra- and inter-observer agreement for ECG classifications.

Kaplan-Meier analysis will be performed to determine the cumulative long-term mortality rates in different ECG subgroups. The mortality across groups will be compared using log-rank test. A Cox-regression model will be used to perform a survival analysis according to intervention timing and revascularization status. Baseline characteristics with a P value of 0.05 or less in the univariate analysis will be included and a step-down procedure will be applied for selection of final covariates.

**Note:** After data collection, we performed a univariate analysis for mortality and found that many of the baseline parameters, including age, systolic blood pressure, heart rate, baseline

creatinine etc., were significantly associated with long-term mortality. But when these were included in the Cox regression analysis alongside with baseline GRACE risk score, they all lost their statistical significance. Considering GRACE risk score already includes almost all of these variables, we only used GRACE risk score as a covariate in Cox regression model.

The sensitivity, specificity and diagnostic accuracy of STE/non-STE or ACO/non-ACO ECG approaches will be calculated using receiver operating characteristics analysis. As these parameters are highly dependent on the pre-test probability of the disease and pre-test probability of ACO and long-term mortality are closely associated with the presentation type, we will also repeat these analyses after weighing cases for the total number of hospital admissions in the study period.

Statistical analyses will be performed with SPSS (version 24.0; SPSS Inc., Chicago, IL) and MedCalc Software (version 18.2.1 [Evaluation version]; MedCalc Software, Ostend, Belgium).

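### The stated 95% power for 10% versus 15% mortality in the NSTEMI group does not follow from the plan's inputs: 963 patients with 25% ACO-MI give about 56%

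*Combined protocol and SAP*

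**What the plan says.** The paragraph headed Estimated number of subjects to be submitted bases the mortality calculation on "the enrollment of 963 patients in non-STE-MI group". It states that this number "would provide the study with a statistical power of 95% to detect a relative excess mortality rate of 5% in ACO-MI subgroup". The remaining inputs follow in the same sentence: "from 10% to 15%) with the use of a two-sided test at the 0.05 level, with a frequency prediction of 25% for ACO-MI".

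Section 2 (Patient selection) sets the cohort sizes: "We planned to enroll 1000 patients in each of the STEMI, NSTEMI and control groups". So 963 is naturally read as the size of the whole NSTEMI cohort, rounded up to 1000, and not as the size of one subgroup.

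The sample-size paragraph names neither a test nor a follow-up time. For mortality, the Statistical Analysis section says: "The mortality across groups will be compared using log-rank test". The same sample-size paragraph gives 267 and 383 patients for the two AUC comparisons, which are sized separately.

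**The concern.** All inputs for a two-group power calculation are given, and they do not lead to 95%. A 25% share leaves only about 241 patients in the smaller group and about 108 expected deaths in total (0.15 × 241 + 0.10 × 722 = 36.2 + 72.2 = 108.4). That is too few for high power against a 5-point difference.

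This calculation underlies the mortality contrast between ACO-MI and non-ACO-MI patients within the NSTEMI group. If readers accept 95% power, they will take a non-significant result as strong evidence against a 5-point excess. On the plan's own inputs, the chance of missing such an excess is near one half.

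There is also a minor wording slip: moving from 10% to 15% is an absolute excess of 5 percentage points (50% in relative terms), but the plan calls it a relative excess of 5%.

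**Working it through.** **Inputs.** From the sample-size paragraph: N = 963; ACO-MI share 25%, so n1 = 241 and n2 = 722; mortality p1 = 0.15 and p2 = 0.10; two-sided alpha 0.05 (z = 1.96). From section 2: planned N = 1000, so 250 and 750. Assumption: 10% and 15% are cumulative mortality at one common time.

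**Power at 963, pooled two-proportion formula.**

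Power = Φ[(|p1 − p2| − 1.96 × SE0) / SE1]

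- Pooled rate = (241 × 0.15 + 722 × 0.10) / 963 = 0.1125
- SE0 = √[0.1125 × 0.8875 × (1/241 + 1/722)] = 0.0235
- SE1 = √[0.15 × 0.85/241 + 0.10 × 0.90/722] = 0.0256
- (0.05 − 1.96 × 0.02351) / 0.02557 = 0.154, and Φ(0.154) = 0.561

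The plan's 95% is not reproduced; the result is **56.1%**.

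**Other methods on the same inputs.**

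| Method (241 vs 722) | Power |
|---|---|
| Chi-square, exact enumeration | 55.6% |
| Log-rank, simulated (exponential survival, common censoring, no loss; 40,000 runs) | 55.6% |
| Arcsine | 53.3% |
| Fisher exact, simulated | about 53% |
| Continuity-corrected | 51.8% |
| Unpooled formula | 49.8% |
| Log-rank, Schoenfeld formula (108 events, hazard ratio ln 0.85 / ln 0.90 = 1.54) | 49.7% |

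The range is about 50% to 56%, so 56% is the favourable end. Loss to follow-up would lower it.

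**At the planned 1000 (250 vs 750).** 57.5% by formula, 57.0% by exact enumeration, 57.9% by simulated log-rank.

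**Size needed for 95%.** At 1:3, n1 = {1.96 × √[0.1125 × 0.8875 × (1 + 1/3)] + 1.645 × √[0.1275 + 0.09/3]}² / 0.05² = (0.7151 + 0.6528)² / 0.0025 = 748.5. Rounding up to 749 and 3 × 749 = 2,247 gives **2,996** patients, about 3.1 times 963. Exact and simulated log-rank power at that size are both 95.2%.

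**What 963 can detect against 10%.** An ACO-MI rate of about 17% with 80% power (exact 80.8%) and about 19.4% with 95% power (exact 95.5%).

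**Precision.** The expected 95% CI half-width for the mortality difference is 1.96 × 0.0256 = 0.050. That is 5.0 points, as wide as the effect itself.

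**Could another reading give 95%?** Pooled formula, two-sided unless stated:

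| Reading | Power |
|---|---|
| Literal 5% relative excess (10% vs 10.5%), 241/722 | 5.8% |
| 963 split equally | 65.1% |
| 963 non-ACO plus 321 ACO | 67.6% |
| 10% is the overall rate (15% vs 8.3%), 241/722 | 81.9% |
| 963 in each group | 91.3% |
| 963 in each group, one-sided | 95.3% |
| 963 ACO plus 2,889 non-ACO | 98.2% |

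The one near-match, 95.3%, contradicts the two-sided test, the 25% share and 963 as the whole group. The last row implies 3,852 NSTEMI patients, against the 1000 planned.

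**The case against.** The strongest counter-argument concerns follow-up time. The sample-size paragraph speaks of a mortality rate, and the plan analyses long-term mortality by Kaplan-Meier and log-rank. If 10% and 15% were annual rates, simulated log-rank power with 241 and 722 patients and no loss would be about 81% at two years, 91% at three and 96% at four. So a figure near 95% can be reached with the stated size, share, alpha and test. But this needs a per-year qualifier and about four years of follow-up, and the available text states neither. A rise from 10% to 15%, given without a time unit, reads more naturally as cumulative risk. What stands is that 56% depends on the cumulative reading, and the corrected statement should say so. Part of the protocol between the sample-size paragraph and section 4 was not available for this review, so a follow-up horizon may be given there.

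It can also be said that little changes in practice. Section 2 describes the STEMI and NSTEMI groups as completed, the Statistical Analysis section reports a mortality analysis done after data collection, and the AUC comparisons, which bear directly on the diagnostic question, have their own sizes. This is fair as far as the design goes. It does not make the power statement correct, and that statement still governs how a null mortality result is read.

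**Conclusion.** The concern holds. On the plan's stated inputs, with 10% and 15% as cumulative mortality and all patients followed to the same point, power is about 56% at 963 patients and about 58% at 1000, not 95%. The type II error is about 44% (100 − 56), where the plan implies 5%. No method applied to those inputs exceeds about 56%, and no alternative reading that respects the text as written reaches 95%. The error is confined to the mortality calculation; the AUC sample sizes were not checked and no claim is made about them. It must be corrected, because it describes a comparison with close to even odds of success as highly powered.

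**What to change.** Replace the mortality power statement with wording such as:

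> With 963 (1000) NSTEMI patients, of whom 25% have ACO-MI, power is about 56% (58%) for cumulative mortality of 15% versus 10% at [follow-up time], using a two-sided [named test] at the 0.05 level. At 963 patients, power is about 80% for 17% versus 10% and about 95% for 19.4% versus 10%.

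Fill in the test and the follow-up time to which the two rates refer. If annual rates were intended, say so, state the follow-up and recompute. Describe the 5% as an absolute excess of 5 percentage points.

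The cost is wording only: no extra patients and no change of test or endpoint. The one drawback is a less favourable stated power. Since enrolment is described as complete, this corrects the justification and not the design.

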### **4. Data Collection**

- 1) Starting from May 1, 2017 hospital database will be screened for STEMI and NSTEMI admissions.
- 2) Following will be checked:
  - The presence of a technically adequate (pre-cath) ECG.
  - A peak troponin level over 99 th percentile.
- 3) ECGs will be printed and handed over to ECG reviewers after all groups are completed.
- 4) Following baseline variables will be entered to the study Excel spreadsheet:  
Enrollment no., protocol no., cohort, age, gender, prior history of MI, prior history of PCI or CABG, presence or absence of diabetes (medication use or HbA1c>6.5), hypertension (medication use or average blood pressure over 140/90 mmHg during hospital stay), dyslipidemia (medication use), smoking (current smoker or past smoker with in 1 year), admission systolic blood pressure, admission heart rate, admission creatinine level, admission hemoglobin level, Killip class on admission, admission troponin I level (from a blood sample collected before, during or just after coronary angiography or at admission to the emergency department), peak troponin level (the maximum troponin level during hospital stay), 24-to-48 hour troponin level (the highest troponin level during this time window), ejection fraction from echocardiogram report, time from ECG to PCI (will be calculated from system recordings), in-hospital mortality, in-hospital resuscitation, in-hospital intubation.
- 5) From these parameters, baseline GRACE risk score, the change within troponin value in the first 24 hours will be calculated.

- 6) Angiograms will be reviewed by angiogram reviewers from hospital digital database. Following points will be noted: (1) the presence of total occlusion. The presence of collaterals to distal vessel, appearance of the total occlusion, easiness of guidewire crossing will also be assessed to determine if the total occlusion is acute in nature. If necessary, primary operator will also be contacted. (2) The presence of culprit lesion, which was defined based on several angiographic properties including appearance, presence of angiographic thrombus, critical stenosis with less than Thrombolysis in Myocardial Infarction 3 flow.

### **ECG Interpretation**

1. **Type 1 EGGs:** New ST-segment elevation at the J-point in two contiguous leads with the cut-point:  $\geq 1$  mm in all leads other than leads V2–V3 where the following cut-points apply:  $\geq 2$ mm in men  $\geq 40$  years;  $\geq 2.5$  mm in men  $< 40$  years, or  $\geq 1.5$  mm in women regardless of age.
  - a. **Type 1a:** The amplitude, morphology, extent of STE and the presence of additional findings (hyperacute T waves, Q-waves, terminal QRS distortion) make ECG highly obvious for MI presumably due to acute, thrombotic occlusion. These ECGs will be included in both STEMI and ACO-MI groups.
  - b. **Type 1b:** Does not meet recommended criteria for STEMI, but highly suggestive for MI, despite being subtle and difficult. Possible findings are minor STE with minor reciprocal ST-depression not fulfilling STEMI criteria, hyperacute T-waves or DeWinter's pattern, subtle anterior STE hard to differentiate from benign variant STE and nonconsecutive STE. These ECGs will be included in ACO-MI group but not in STEMI group.
  - c. **Type 1c:** There is ST-segment elevation that meets criteria for STEMI, but it is

uncertain whether it is due to MI or to another condition, such as benign variant STE, left ventricular hypertrophy, left bundle branch block, prior MI, pericarditis, etc. These ECGs will be included in STEMI group but not in ACO-MI group, unless there are additional findings suspicious for acute coronary occlusion as follows:

- i. Differential diagnosis for benign variant STE: Type 1c, if fulfills STEMI criteria. But re-classified as Type 1b, if Aslanger's formula is positive.
  - Aslanger's formula:  $(R\text{-wave amplitude in lead V4} + QRS \text{ amplitude in V2}) - (QT \text{ interval in millimeters} + STE_{60} \text{ in V3}) < 12$
  - *Reference:* Aslanger E, Yıldırım Türk Ö, Bozbeyoğlu E, et al. A Simplified Formula Discriminating Subtle Anterior Wall Myocardial Infarction from Normal Variant ST-Segment Elevation. *Am J Cardiol* 2018; 122: 1303-9.
- ii. Differential diagnosis for left ventricular hypertrophy
  - Type 1c unless ST segment to R-S-wave magnitude is equal or greater than 25% (then indicates ACO, Type 1b).
  - *Reference:* Armstrong EJ, Kulkarni AR, Bhave PD, et al. Electrocardiographic criteria for ST-elevation myocardial infarction in patients with left ventricular hypertrophy. *Am J Cardiol* 2012; 110: 977-83.
- iii. Differential diagnosis for isolated left bundle branch block:
  - Coded as Type 1c, unless one of the modified Sgarbossa criteria is positive (then indicates ACO, Type 1b):
  - $\geq 1$  lead with  $\geq 1$  mm of concordant ST elevation

- $\geq 1$  lead of V1-V3 with  $\geq 1$  mm of concordant ST depression
- $\geq 1$  lead anywhere with  $\geq 1$  mm STE and proportionally excessive discordant STE, as defined by  $\geq 25\%$  of the depth of the preceding S-wave.
- *Reference:* Smith SW, Dodd KW, Henry TD, Dvorak DM, Pearce LA. Diagnosis of ST Elevation Myocardial Infarction in the Presence of Left Bundle Branch Block using the ST Elevation to S-Wave Ratio in a Modified Sgarbossa Rule. *Ann Emerg Med* 2012; 60: 766-76

iv. Differential diagnosis for prior MI:

- Type 1c, unless Smith's rule is positive (then indicates ACO, Type 1b):
- Smith's rule: If any 1 lead between V1-V4 has a T-wave amplitude to QRS amplitude ratio greater than or equal to 0.36.
- *Reference:* Klein LR, Shroff GR, Beeman W, Smith SW. Electrocardiographic criteria to differentiate acute anterior ST-elevation myocardial infarction from left ventricular aneurysm. *Am J Emerg Med* 2015; 33:786-90.

v. Differential diagnosis for pericarditis:

- Type 1c, unless there is ST-depression in aVL (then indicates ACO, Type 1b).
- *Reference:* Bischof JE, Worrall C, Thompson P, Marti D, Smith SW. ST depression in lead aVL differentiates inferior ST-elevation myocardial infarction from pericarditis. *Am J Emerg Med*. 2016; 34: 149-54.

- d. **Type 1d:** There is ST-segment elevation that meets criteria for STEMI, but there is also T-wave inversion indicative of spontaneous reperfusion or QS waves and T-wave inversion indicative of subacute MI. These ECGs are not excluded by STEMI criteria, therefore will be included in STEMI group but not in ACO-MI group.
2. **Type 2 ECGs:** ECG that meets acute myocardial ischemia criteria recommended by fourth universal definition of MI. The ECG has "primary", i.e. cannot be completely explained as secondary to a depolarization disorder, ST-segment depression or T-wave inversion that is nondiagnostic of STEMI but is diagnostic of myocardial ischemia. These ECGs will not be included in neither STEMI nor ACO-MI groups.
3. **Type 3 ECGs:** Nonspecific ECG that is abnormal but nondiagnostic of any kind of acute coronary syndrome. Minor abnormalities including left ventricular hypertrophy without ST-T changes, arrhythmias, impulse generation and conduction diseases etc. These ECGs will not be included in neither STEMI nor ACO-MI groups.
4. **Type 4 ECGs:** Completely normal ECG. These ECGs will not be included in neither STEMI nor ACO-MI groups.

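### Type 1c sub-rules move ECGs that meet STEMI criteria into a class defined as not meeting them, so the STEMI result depends on the competing ACO rule

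*Combined protocol and SAP*

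**What the plan says.** The ECG Interpretation section sorts ECGs into classes and assigns each class to the STEMI group, the ACO-MI group, both or neither.

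- **Type 1b:** "Does not meet recommended criteria for STEMI, but highly suggestive for MI, despite being subtle and difficult". Its assignment is "These ECGs will be included in ACO-MI group but not in STEMI group".
- **Type 1c:** ST elevation that meets STEMI criteria but may have another cause. It counts as STEMI and not ACO-MI, unless further findings suggest occlusion.
- **Type 1c sub-rules i to v** (benign variant, left ventricular hypertrophy, left bundle branch block, prior MI, pericarditis): a positive discriminator changes the code to Type 1b. Sub-rule i reads "Type 1c, if fulfills STEMI criteria. But re-classified as Type 1b". Sub-rule v reads "Type 1c, unless there is ST-depression in aVL (then indicates ACO, Type 1b".
- **Type 1d:** meets STEMI criteria but shows signs of reperfusion or subacute MI. "These ECGs are not excluded by STEMI criteria, therefore will be included in STEMI group but not in ACO-MI group".

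Section 2, Patient selection, defines the STEMI cohort without reference to any ACO rule: "These patients should have all of the following criteria: (1) New ST-segment elevation at the J-point in two contiguous leads", plus troponin and clinical picture. The classes feed the head-to-head comparison in Statistical Analysis: "The sensitivity, specificity and diagnostic accuracy of STE/non-STE or ACO/non-ACO ECG approaches will be calculated using receiver operating characteristics analysis".

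**The concern.** An ECG cannot both meet and not meet the same cut-points, yet the sub-rules send ECGs from a class that meets them to one that does not. In practice the ECG leaves the STEMI group because the ACO rule is positive. The comparator's result is then partly set by the approach it is being compared with.

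Each true occlusion among these ECGs becomes a false negative for STEMI and stays a true positive for ACO-MI. The study's stated objective is to learn whether the ACO approach identifies patients better than STEMI criteria. A coding rule that removes double-positive ECGs from one side could inflate the apparent sensitivity advantage of the other. The same coding also enters any survival comparison by ECG subgroup.

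**Working it through.** **Class definitions side by side**

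| ECG | Meets STEMI cut-points | STEMI group | ACO-MI group |
|---|---|---|---|
| 1a | yes | yes | yes |
| 1b | no | no | yes |
| 1c, rule negative | yes | yes | no |
| 1c, rule positive, re-coded 1b | yes | **no** | yes |
| 1d | yes | yes | no |

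The fourth row is the only one where the ECG meets the cut-points and is not counted as STEMI. It conflicts with the reason given for Type 1d, which stays in the STEMI group because the criteria do not exclude it. No existing class fits: Type 1a counts in both groups but is reserved for obvious MI. A rule-positive ECG without qualifying ST elevation, such as bundle branch block with only concordant ST depression, belongs in Type 1b and is not at issue.

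**Direction**

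Let k be the number of ECGs re-coded, p their ACO frequency, N1 the ACO patients and N0 the non-ACO patients. For a yes/no test, AUC = (sensitivity + specificity)/2.

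- Change in sensitivity = −kp/N1, never positive.
- Change in specificity = +k(1−p)/N0, never negative.
- Change in AUC = ½[k(1−p)/N0 − kp/N1], negative exactly when p > N1/(N1+N0), the sample prevalence.

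The ACO-MI call is the same under either code, so any change in STEMI AUC passes in full into the difference between approaches.

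**Illustration**

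From the documents: 1000 patients per group (section 2, Patient selection) and ACO in 25% of NSTEMI (Estimated number of subjects). Assumed: ACO in 85% of STEMI and 0% of controls, and before re-coding the STEMI cohort and only that cohort is STEMI-positive.

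N1 = 850 + 250 = 1100; N0 = 3000 − 1100 = 1900. Baseline sensitivity 850/1100 = 0.773, specificity 1750/1900 = 0.921, AUC 0.847. Break-even p = 1100/3000 = 36.7%.

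| k | p | Change in STEMI AUC |
|---|---|---|
| 20 | 60% | −0.003 |
| 50 | 80% | −0.016 |
| 100 | 80% | −0.031 |
| 100 | 95% | −0.042 |
| 100 | 30% | +0.005 |
| 100 | 20% | +0.012 |

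For k = 50 and p = 80%: sensitivity 810/1100 = 0.736, specificity 1760/1900 = 0.926, AUC 0.831. Varying the assumed ACO frequency over 70–95% in STEMI and 20–33% in NSTEMI gives −0.013 to −0.020 for this case. For scale, the sample-size section plans for an AUC difference of 0.770 − 0.700 = 0.070, and 0.0156/0.070 is about 22%.

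**Re-coded controls**

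Controls who meet the cut-points can be re-coded too, which lowers the pooled p. Adding 59 controls to the 50 ECGs above gives 40/109 = 36.7% and no AUC change.

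**Weighted analysis**

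Section 2 states "This institution also receives STEMI and NSTEMI patients with a 2:1 ratio", so STEMI has weight 1 and NSTEMI 0.5. The control weight w is assumed. N1 = 850 + 125 = 975; N0 = 150 + 375 + 1000w.

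| w | N0 | Break-even p | 50 re-coded at 80%, no controls | Same plus 59 controls |
|---|---|---|---|---|
| 1 | 1525 | 39.0% | −0.017 | ½(69/1525 − 40/975) = +0.002 |
| 2 | 2525 | 27.9% | −0.019 | ½(128/2525 − 40/975) = +0.005 |
| 5 | 5525 | 15.0% | −0.020 | ½(305/5525 − 40/975) = +0.007 |

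**The case against.** The strongest reply is that the exception in the Type 1c lead-in qualifies only the exclusion from ACO-MI. Rule-positive ECGs would then count in both groups, and the Type 1b label would be shorthand for ACO-positive. That may well have been the intention. But the sub-rules name Type 1b, whose exclusion from the STEMI group is explicit, and nothing in the documents says these ECGs stay STEMI-positive. A reader coding from the text would do the opposite. The point is therefore about the written rule, not proof of how ECGs were coded.

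Three further points stand and limit the concern:

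- Section 2 defines the enrolment cohort, which is a different variable from the later ECG class. Cohort membership is unaffected, and so is the mortality sample size if it refers to the enrolled NSTEMI cohort. The conflict with section 2 is that one label, the STEMI group, carries two meanings.
- Cohort is a recorded variable, so troponin-positive patients who met the cut-points but were coded 1b can be found by cross-tabulation. Controls cannot.
- The net direction for AUC is not established. The sub-rules' wording that a positive result indicates ACO suggests a high p, but it is not a measured predictive value, and enough re-coded controls would cancel or reverse the AUC loss. The fall in sensitivity is not open to this reply: it occurs whenever any re-coded ECG is a true ACO.

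**Conclusion.** The coding is wrong as written and should be corrected before the accuracy comparison is relied on. The contradiction follows from the class definitions alone and needs no assumption. Under the literal rule STEMI sensitivity can only fall and its specificity can only rise. STEMI AUC falls when the ACO frequency among re-coded ECGs exceeds prevalence and rises when it is below.

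The size for this study is unknown. In the unweighted illustration, 20 to 100 re-coded ECGs with 60–95% ACO cost the STEMI approach 0.003 to 0.042 in AUC. Those counts and frequencies, and the 85% and 0% ACO frequencies behind them, are assumptions. The losses also assume that no controls are re-coded. Bias in AUC towards the ACO approach is therefore possible, not shown.

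**What to change.** 1. Record two separate variables for every ECG: STEMI status from the ST-elevation cut-points alone, and ACO-MI status from the ACO findings.
2. Give Type 1c ECGs with a positive discriminator their own code (for example Type 1e: meets STEMI criteria, ACO rule positive), counted in both groups, and put it in place of Type 1b in sub-rules i to v. An explicit sentence keeping these ECGs STEMI-positive would do the same job.
3. Reserve Type 1b for ECGs below the cut-points, including rule-positive ECGs without qualifying ST elevation. Since Type 1b sits under a Type 1 heading that itself states the cut-points, reword that heading.
4. State in Statistical Analysis that STE/non-STE comes from the cut-point variable. Report how many ECGs carry the new code, by cohort, and their ACO frequency.

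The cost is a wording change and re-labelling of ECGs already held; no new patients or tests are needed. The Data Collection list has no field for ST amplitude or STEMI-criteria status, so some Type 1b ECGs, mainly in controls, may have to be looked at again. STEMI specificity will be equal to or lower than under the literal coding, and the apparent sensitivity advantage of the ACO approach may shrink.

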### **ACO Adjudication**

Because the infarct-related artery may spontaneously open by the time of the angiogram or total occlusion may be chronic in nature, we defined a composite ACO using following criteria:

(1) total occlusion or presence of culprit lesion on angiography

PLUS

a peak troponin I level equal to or greater than 1.0 ng/ml

PLUS

at least 20% rise within 24 hours

(2) a highly elevated peak troponin, i.e., peak troponin I > 5.0 ng/mL, which was shown to be highly correlated with ACO

(3) cardiac arrest before any troponin rise has been documented with supporting clinical evidence of possible ACO.

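### Type 1d ECGs are coded ACO-negative, but the ACO reference standard counts many of the same infarcts as ACO; accuracy should be shown with Type 1d separate and coded both ways

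*Combined protocol and SAP*

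**What the plan says.** **Index test.** In the combined protocol and SAP, ECG Interpretation, Type 1d is a tracing that meets STEMI criteria but also shows "T-wave inversion indicative of spontaneous reperfusion or QS waves and T-wave inversion indicative of subacute MI". Its coding is explicit: "These ECGs are not excluded by STEMI criteria, therefore will be included in STEMI group but not in ACO-MI group".

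**Reference standard.** ACO Adjudication explains why a composite is used: "Because the infarct-related artery may spontaneously open by the time of the angiogram or total occlusion may be chronic in nature". Criterion 1 needs "total occlusion or presence of culprit lesion on angiography", together with "a peak troponin I level equal to or greater than 1.0 ng/ml" and "at least 20% rise within 24 hours". Criterion 2 is "a highly elevated peak troponin, i.e., peak troponin I > 5.0 ng/mL, which was shown to be highly correlated with ACO", with no condition on patency or timing. Criterion 3 concerns cardiac arrest before a documented troponin rise. I read the three as alternatives. The word 'or' is not printed, but criterion 3 could not sensibly be required together with the other two.

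**Analysis.** Statistical Analysis compares the STE and ACO approaches by ROC methods, and repeats this with weights for total admissions. It has no rule, exclusion or sensitivity analysis for Type 1d. The section on the estimated number of subjects plans for an AUC contrast of 0.700 against 0.770.

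**The concern.** The two sides of the accuracy comparison have different targets. The ACO reading of a Type 1d tracing amounts to saying that the artery is no longer acutely occluded. The composite does not ask that question. It accepts a culprit lesion without total occlusion, or a high troponin peak alone, so it cannot separate an artery already open when the ECG was taken from one that opened between ECG and angiogram. Both are labelled ACO.

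A reader who correctly recognises a reperfused infarct is therefore marked wrong whenever the composite is met, and STEMI criteria are marked right on the same tracing. What is at stake is the ACO approach's sensitivity and the AUC difference between the two approaches, which bear directly on the question in the Study Project Summary. Reweighting by admissions does not change how any patient is classified, so it does not remove the mismatch.

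**Working it through.** The documents give no figure for Type 1d, so there is nothing to reproduce. The first step is logical; the second is an illustration under stated assumptions.

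**Step 1: classification of a Type 1d patient**

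| Composite result | ACO approach (reads negative) | STEMI criteria (read positive) |
|---|---|---|
| Met | False negative | True positive |
| Not met | True negative | False positive |

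Which row applies depends on the kind of infarct:

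- *Reopened artery:* can be positive by criterion 1 (culprit lesion, peak of at least 1.0 ng/mL, 20% rise) or by criterion 2.
- *Subacute infarct with flat or falling troponin:* fails the 20% rise in criterion 1, so it becomes positive through criterion 2 if the peak exceeds 5.0 ng/mL.
- *Peak of 1.0 to 5.0 ng/mL without a 20% rise, or peak below 1.0 ng/mL:* negative on criteria 1 and 2.

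**Step 2: size**

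Let T be the number of Type 1d ECGs, q the share of them that meet the composite, D the number of reference-positive patients, and N the total. Coding Type 1d ACO-negative rather than ACO-positive changes the ACO approach as follows:

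- Sensitivity loss = T × q / D
- Specificity gain = T × (1 − q) / (N − D)
- For a yes/no test AUC = (sensitivity + specificity) / 2, so AUC loss = (sensitivity loss − specificity gain) / 2

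STEMI criteria read Type 1d as positive either way, so the AUC difference between approaches moves by the same amount.

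*Break-even.* The ACO approach loses AUC when q / D > (1 − q) / (N − D), which simplifies to q > D / N, the overall ACO prevalence.

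*Inputs.*

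- N = 3000: three groups of 1000 (Patient selection).
- D = 1100: 85% of 1000 STEMI patients (assumed), plus 25% of 1000 NSTEMI patients, with no controls counted (assumed). The 25% is the ACO-MI frequency in the sample-size paragraph. The plan also uses ACO-MI for an ECG class, so reading it as a reference-positive rate is an assumption too.
- T = 50 to 150: 5% to 15% of the STEMI group (assumed).
- q = 0.85 to 0.95 (assumed).

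Here N − D = 1900 and break-even is 1100 / 3000 = 0.37.

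| T | q | Sensitivity loss | Specificity gain | AUC loss |
|---|---|---|---|---|
| 50 | 0.85 | 42.5/1100 = 0.039 | 7.5/1900 = 0.004 | 0.017 |
| 50 | 0.95 | 47.5/1100 = 0.043 | 2.5/1900 = 0.001 | 0.021 |
| 150 | 0.85 | 127.5/1100 = 0.116 | 22.5/1900 = 0.012 | 0.052 |
| 150 | 0.95 | 142.5/1100 = 0.130 | 7.5/1900 = 0.004 | 0.063 |

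The AUC loss is between about a quarter (0.017 / 0.070) and nine-tenths (0.063 / 0.070) of the planned contrast.

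*Wider assumptions.* With T = 50 to 200, q = 0.50 to 0.95, D = 1000 to 1400 and N = 3000, sensitivity falls by 1.8 to 19.0 points, specificity rises by 0.1 to 6.3 points, and AUC falls by 0.001 to 0.093. Break-even then lies between 0.33 and 0.47. The size is therefore unknown until Type 1d is counted.

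**The case against.** The strongest reply is that the coding is deliberate. The plan states its reason: STEMI criteria do not exclude these tracings, and the ACO approach does. That is part of the index test being proposed. It also probably works against the investigators' own hypothesis, so it would not manufacture a superiority claim. Recoding Type 1d as positive in the main analysis would favour that hypothesis, and the note in Statistical Analysis shows that data collection is already complete. This stands. It is why the stated coding should remain the main analysis.

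Three stronger readings are tempting, and the documents do not support them:

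- *A reader might infer that every Type 1d ECG pushes the comparison one way.* It does not. Patients who fail the composite credit the ACO approach and count against STEMI criteria.
- *A reader might infer that the composite counts subacute infarcts generally.* ACO Adjudication names reopened arteries, not subacute infarction, and the 20% rise excludes late presenters with flat or falling troponin from criterion 1.
- *A reader might infer that the mismatch alone could produce a finding of no advantage.* That is not shown. On the narrower assumptions the largest AUC loss, 0.063, is below 0.070. The wider range does exceed 0.070, but only with inputs the plan does not give. Nor does the plan say whether the forecast of 0.770 already allows for the Type 1d coding.

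What the reply does not remove is the mismatch itself. If Type 1d means not occluded now, the composite does not measure that, and a bias against the hypothesis still distorts the reported accuracy.

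**Conclusion.** The inconsistency between ECG Interpretation and ACO Adjudication is explicit for reopened arteries. For subacute infarcts with flat or falling troponin it follows from the peak criterion of more than 5.0 ng/mL. Statistical Analysis does not deal with either. The direction is against the ACO approach if the composite-positive share of Type 1d exceeds ACO prevalence, which is likely but cannot be confirmed from the documents. The likely consequence is a hidden or understated ACO advantage, not a spurious one.

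Confidence is high on the coding conflict and low on its size, since the Type 1d count, its composite-positive share and the number of reference-positives all had to be assumed. The point supports an inexpensive addition to the analysis plan. It does not show that the design is invalid or that the index test must be redefined.

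**What to change.** Add to Statistical Analysis:

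1. Keep Type 1d as ACO-negative and STEMI-positive in the main accuracy analysis.
2. Show Type 1d as its own row in the cross-tabulation of ECG type against the composite, so that T and q can be read directly.
3. Add two sensitivity analyses against the composite: Type 1d coded ACO-positive, and Type 1d set aside for both approaches.
4. As a secondary analysis in catheterised patients only, labelled as such, report both approaches against acute total occlusion at angiography. Data Collection item 6 already records total occlusion and the features used to judge whether it is acute.
5. State whether the direction of the comparison is the same across all of these, and date the addition, since data collection is complete.

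The cost is plan wording and a few extra runs on existing data. The conclusion may be less clear-cut if the codings disagree. The secondary reference has its own limits: Patient selection allows patients without catheterisation, so it covers a selected subset, and it misses arteries that were occluded at the ECG but had reopened by angiography, which is the problem the composite was written to address. It should therefore supplement the composite, not replace it.
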